#### 6.1.2 INVESTIGATIONAL PRODUCT CAUSALITY AND SEVERITY

Relationship of an AE to investigational product will be assessed as follows:

- **Definite:** There is a clinically plausible time sequence between the onset of the AE and the administration of investigational product; when the event responds to withdrawal of investigational product and/or recurs with readministration of investigational product
- **Probable:** There is a clinically plausible time sequence between the onset of the AE and the administration of investigational product; the AE is unlikely to be caused by the concurrent/underlying illness, other drugs or procedures
- **Possible:** There may or may not be a clinically plausible time sequence between the onset of the AE and the administration of investigational product and a cause cannot be ruled out
- **Unrelated:** There is not a temporal or causal relationship to investigational product administration

The Investigator is responsible for evaluating all AEs and determining the severity of the event. Severity will be categorized as mild, moderate or severe according to the following definitions:

• Mild: Event may be noticeable to subject; does not influence daily activities; usually does not require intervention

- Moderate: Event may be of sufficient severity to make subject uncomfortable; performance of daily activities may be influenced; intervention may be needed
- Severe: Event may cause severe discomfort; usually interferes with daily activities; subject may not be able to continue in the trial; treatment or other intervention usually needed

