### 3.1.1 DURATION OF TRIAL

The duration is up to 38 weeks on trial, including a screening period of up to two weeks followed by a single treatment and a follow-up period of up to 36 weeks post-treatment. All subjects will be followed for at least 24 weeks post-treatment.

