# 4.2.5 FINAL EVALUATION VISIT OR EARLY DISCONTINUATION

The following procedures must be performed and recorded at the Final Evaluation Visit for each subject. Following treatment, subjects will be followed for safety until at least Week 24 and up to Week 36 with monthly visits until both IGA-FWS and PFWS scores have returned to baseline. The subject will then have a Final Evaluation Visit.

- 1. Conduct patient education: Discuss the potential effect of DaxibotulinumtoxinA for Injection treatment, explain the PFWS measurement and the categories of the severity assessment scales, and instruct the subjects to consider depth of lines for severity of their glabellar lines. Use the provided Patient Education Brochure
- 2. Measure and record vital signs (body temperature, respiratory rate, sitting radial pulse, and sitting systolic and diastolic blood pressure)

If there are no safety concerns, the subject's participation in the trial is complete at this visit.

After the Final Evaluation Visit, all qualified subjects will have the option to enroll into an open-label, trial to evaluate the long-term safety of repeat use of DaxibotulinumtoxinA for Injection for the treatment of moderate to severe glabellar lines.

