4.8.1. Extent of Exposure

All patients receive one administration of investigational product. The sum of volume of investigational product injected and the volume of investigational product injected at each of the five injection sites will be summarized by treatment group using descriptive statistics (number of non-missing observations, mean, median, minimum, maximum, and standard deviation).

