4.8.3. Adverse Events

All treatment-emergent AEs (TEAEs) will be listed and summarized by treatment group, system organ class, preferred term, severity, relationship, and seriousness. Serious adverse events (SAEs) will be summarized by treatment group, severity, and relationship to study treatment and will be listed by patient separately.

Each patient will be counted only once within a system organ class or a preferred term using the event with the greatest relationship and greatest severity.

Specific AF will be summarized by treatment group, system organ class, and preferred term. Adverse events included will be those listed in the query from Section 3.3.2.

All information pertaining to AEs noted during the trial will be listed by patient, detailing the verbatim description given by the Investigator, preferred term, system organ class, start date, stop date, severity, action taken regarding study drug, corrective treatment, outcome, and drug

relatedness. The event onset will also be shown relative (in number of days) to the date of first study treatment administration. In addition, a list of patients who prematurely discontinue from the trial due to adverse events will also be provided.

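### The Definite causality level cannot be reached after a single injection, and the boundary between Possible and Unrelated is ambiguous

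*Protocol*

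**What the plan says.** Protocol 6.1.2 sets four levels of relationship to investigational product:

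- **Definite:** plausible timing, and it applies "when the event responds to withdrawal of investigational product and/or recurs with readministration of investigational product".
- **Probable:** plausible timing, and "the AE is unlikely to be caused by the concurrent/underlying illness, other drugs or procedures".
- **Possible:** timing is left open ("There may or may not be a clinically plausible time sequence between the onset of the AE and the administration of investigational product"), with the further condition that causation has not been excluded.
- **Unrelated:** neither link is described as present ("There is not a temporal or causal relationship to investigational product administration").

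Exposure is a single treatment. Protocol 3.1.1 describes screening "followed by a single treatment and a follow-up period of up to 36 weeks post-treatment", and SAP 4.8.1 states: "All patients receive one administration of investigational product". Repeat use belongs to a different study: under Protocol 4.2.5, once a subject has finished this trial, "all qualified subjects will have the option to enroll into an open-label, trial to evaluate the long-term safety of repeat use".

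Relationship to study drug is part of both adverse-event safety endpoints in Protocol 7.3 and SAP 3.3.1. SAP 4.8.3 summarises treatment-emergent events by relationship and counts each patient once per system organ class or preferred term, "using the event with the greatest relationship and greatest severity". Protocol 7.6.1 has the same counting rule.

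**The concern.** The test for Definite is a dechallenge/rechallenge test, which suits a product that is given repeatedly and can be stopped. Here there is no continuing product to withdraw and no second administration. Protocol 4.5.6 has the injection sites examined after treatment specifically to detect an immediate reaction, and Protocol 6.1 requires clinically significant changes in that evaluation to be reported as adverse events. Even such an event cannot meet the written test.

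At the other end, Possible does not require plausible timing, while Unrelated is worded around the lack of a temporal or causal link. It is not clear whether lacking one of the two is enough.

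What is at stake is one component of a stated safety endpoint. The top row of the relationship tables would be empty by definition, or filled only where an investigator departs from the definition. Coding at the bottom of the scale would depend on how each investigator reads one sentence, across up to 15 centers. The investigator's causality assessment also goes on the serious adverse event form (Protocol 6.3).

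**Working it through.** The documents state no figure on this point, so the check is a logical one: can every kind of event be placed on exactly one level?

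**Attributes, taken from the definitions in Protocol 6.1.2**

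- T: timing is plausible.
- A: other causes are unlikely.
- C: the product cannot be ruled out as a cause.
- D: a response to withdrawal, or recurrence on readministration, has been observed.

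**Assumptions.** A implies C. D implies both T and C. The unnamed cause in the definition of Possible is the product.

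**Definitions in these terms**

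- Definite = T and D.
- Probable = T and A.
- Possible = C.
- Unrelated = not T and not C if both links must be absent, or not T or not C if either absence is enough.

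**Step 1: admissible profiles.** Without D, the pair (A, C) can take 3 values (yes/yes, no/yes, no/no) and T can take 2, giving 3 × 2 = 6. With D, T and C are fixed at yes and A is free, giving 2 more. The total is 8 if D can occur. With one injection (SAP 4.8.1) D cannot occur, and 6 remain.

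**Step 2: Definite.** It is reached by 2 of 8 profiles where D is possible and by 0 of 6 here. The two lost profiles have T and C, so they drop to Probable (if A holds) or to Possible (if not). Neither drops to Unrelated.

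**Step 3: the six remaining profiles** (1 = yes, 0 = no)

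| T | A | C | Levels met if both links must be absent for Unrelated | Levels met if either absence is enough |
|---|---|---|---|---|
| 1 | 1 | 1 | Probable, Possible | Probable, Possible |
| 1 | 0 | 1 | Possible | Possible |
| 1 | 0 | 0 | none | Unrelated |
| 0 | 1 | 1 | Possible | Possible, Unrelated |
| 0 | 0 | 1 | Possible | Possible, Unrelated |
| 0 | 0 | 0 | Unrelated | Unrelated |

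If both links must be absent, 0 of 6 profiles meet both Possible and Unrelated, but 1 of 6 meets no level: plausible timing with the product excluded, such as an intercurrent illness with a clear other cause that starts soon after treatment. If either absence is enough, that gap closes, but 2 of 6 profiles meet both levels.

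On both readings the Probable profile also meets Possible, and Protocol 6.1.2 does not say that the higher level is taken. The greatest-relationship rule in SAP 4.8.3 does not supply this. It chooses among a patient's events after coding, not among levels for one event.

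These are counts of logical profiles, not of events, and say nothing about frequency.

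**The case against.** The strongest reply has four parts.

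1. **Fading of the toxin effect could be read as withdrawal**, which would make Definite reachable. The visible text does not say this. If some centers read it so and others do not, the same event would be coded differently by site.
2. **On the ordinary reading, Possible and Unrelated do not overlap**, because they are separated by whether the cause can be ruled out. This stands: the overlap holds on one reading only. A reader might infer that every event without plausible timing is open to both codes. That is wrong on either reading, because such an event with the product excluded is Unrelated only. The ordinary reading still leaves the gap shown above.
3. **An empty Definite level does little harm.** This stands for any pooled count: events move down to Probable or Possible, never to Unrelated. A reader might infer that the relationship endpoint as a whole is misclassified by construction. The documents do not support that. They also show no related/unrelated grouping in the visible text, but the SAP table shells are not shown and parts are redacted, so its absence cannot be held against the plan.
4. **The main safety comparison does not use the scale.** This stands. Protocol 7.6.1 compares arms by subjects with one or more treatment-emergent events whatever the relationship. Injection-site findings are tabulated separately without causality coding (SAP 4.8.2), investigators are blinded (Protocol 3.1.3), and the safety analysis is descriptive.

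**Conclusion.** The concern holds in a limited form. Read literally, Definite cannot be assigned in this trial, so that level is 0 in both arms by definition and carries no information about causality. The boundary between Possible and Unrelated is ambiguous: it gives either an overlap or a gap, depending on the reading.

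The consequence is confined to descriptive safety reporting by relationship level. Frequency and severity of treatment-emergent events, the primary endpoint, the type I error rate and power do not depend on the scale. A count pooling Definite, Probable and Possible would not change because Definite is empty. The ambiguity at the lower boundary could change such a count, but the documents give no basis for sizing this.

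The conclusion rests on the ordinary meaning of withdrawal and readministration, on the assumptions listed in the working, and on no redacted text redefining the levels. It is worth correcting because relationship is named in the safety endpoints and the correction is cheap.

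**What to change.** In Protocol 6.1.2:

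- **Definite:** replace the withdrawal/readministration test with a criterion that can be met after one administration, namely plausible timing and no other reasonable cause, worded to be distinct from Probable (where other causes are only unlikely).
- **Unrelated:** define it as a causal link to the product being ruled out.
- **Possible:** keep it for any event where the product cannot be ruled out as a cause, whatever the timing, and name the product as the cause in question.
- **Assignment:** state that the highest level met is the one recorded.

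With these changes, the four profiles with C = 1 are coded Possible or higher and the two with C = 0 are Unrelated. All six (4 + 2) are then placed, each on one level.

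Requiring plausible timing for Possible looks like a simpler repair, but it should be avoided. The two profiles with implausible timing and a product that cannot be excluded would become Unrelated or would fit no level.

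The cost is rewording the definitions and briefing the sites so that all code the same way. No new data are needed.

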#### 6.2 REPORTING ADVERSE EVENTS

The Investigator will assess subjects post-treatment and at each subsequent trial visit for the occurrence of AEs. In order to avoid bias in eliciting AEs, subjects should be asked the following non leading question: "How have you felt since your last visit?" All AEs (serious and non-serious) reported by the subject must be recorded on the source documents and CRFs.

In addition, an Investigator must report an SAE to Revance within 24 hours of their awareness of the event according to the procedure outlined below. All fatal or life-threatening SAEs should be telephoned to Revance or the authorized representative as soon as the investigator learns of the event.

## 6.3 SERIOUS ADVERSE EVENTS

An Investigator must report an SAE to Revance or the designated CRO's authorized representative within 24 hours of their awareness of the event:

- 1. Complete and return an SAE Form with all information known to date; including the investigator's assessment of causality.
- 2. If the event is fatal or life-threatening, telephone Revance or the authorized representative as soon as the investigator learns of the event.
- 3. Obtain and maintain all pertinent medical records (discharge summary, autopsy report, etc.) and medical judgments of medical personnel who assisted in subject's treatment and follow-up.
- 4. Provide follow-up information to Revance or the authorized representative.

Regulatory authorities, IRBs/IEC, and Investigators will be notified of SAEs in accordance with applicable regulations and requirements (e.g., GCPs, ICH Guidelines, national regulations and local requirements).

## 6.4 PROCEDURE FOR ACCESSING THE RANDOMIZATION CODE

All subjects will receive DaxibotulinumtoxinA for Injection or placebo. The investigators and trial center staff do not have access to the randomization code. Unblinding randomization codes are maintained by the unblinded statistician in a locked location.

In case of a serious adverse event where knowledge of the subject's treatment is required for the subject's clinical care and safety, the identity of the treatment administered may be requested. The Investigator must contact Revance by telephone with an explanation of the need for obtaining the subject's study treatment information. Documentation of accessing the randomization code should be recorded in the subject's medical record with the date and time the randomization code was accessed, and the names of the personnel involved.

#### 6.5 FOLLOW-UP OF ADVERSE EVENTS

## 6.5.1 FOLLOW-UP OF NON-SERIOUS ADVERSE EVENTS

Non-serious AEs that are identified during the last scheduled trial visit (or early discontinuation, if applicable) must be recorded on the AE CRF as ongoing.

Any clinically significant abnormal test results, e.g., laboratory findings, at the final assessment should be followed to resolution or until determined by the Investigator to be stabilized. Repeat tests may be indicated to establish this.

If a subject has any clinically significant, trial-related abnormalities at the end of the trial, the Medical Monitor should be notified and every effort made by the Investigator to arrange follow up evaluations at appropriate intervals to document the course of the abnormalities.

#### 6.5.2 FOLLOW-UP OF POST TRIAL SERIOUS ADVERSE EVENTS

SAEs that are identified on the last scheduled contact (or early discontinuation, if applicable) must be recorded on the AE CRF page and reported to the CRO and Revance according to the reporting procedures outlined in Section 6.3. This may include unresolved previously reported SAEs, or new SAEs. The Investigator should follow these SAEs until the events are resolved, or the subject is lost to follow-up. The Investigator should continue to report any significant follow-up information to the Medical Monitor, Revance and the IRB/IEC up to the point the event has been resolved. Resolution means the subject has returned to the baseline state of health, or the Investigator does not expect any further improvement or worsening of the subject's condition.

Any new SAEs reported by the subject to the Investigator that occur after the last scheduled contact and are determined by the Investigator to be reasonably associated with the administration of investigational product should be reported to Revance and the IRB/IEC.

#### 7 STATISTICAL ANALYSIS

#### 7.1 GENERAL CONSIDERATIONS

The analysis of data from the trial will be performed when all subjects have completed the trial or discontinued prematurely, and all data are in the database and have been cleaned and verified. All statistical programming will be performed using statistical analysis system (SAS) version 9.4 or higher.

A Statistical Analysis Plan, describing all statistical analyses, will be provided as a separate document prior to database lock and unblinding of the study treatments.

#### 7.2 ANALYSIS POPULATIONS

All subjects who are randomized and receive treatment will be included in the Intent-to-Treat (ITT) population. The summaries will be by treatment as randomized.

All subjects who are randomized, receive treatment, and have provided at least one post-treatment safety assessment will be included in the safety population. The summaries will be by treatment actually received.

The Per-Protocol (PP) population will include subjects from the ITT population who complete the 4-week evaluation without a major protocol violation.

#### 7.3 TRIAL ENDPOINTS

[figure not shown]
Unless specified otherwise, all endpoints associated with IGA-FWS, PFWS, GAIS, or Subject's Diary, henceforth will be based on assessments at maximum frown.

## **Primary Efficacy Endpoint**:

The primary efficacy endpoint of the trial is the proportion of responders with the response defined as

Achieving a score of 0 or 1 (none or mild) and an improvement of at least two
points from baseline on both IGA-FWS and PFWS scales concurrently at Week 4

Henceforth in the document, the response defined above in the primary efficacy endpoint will be abbreviated as "2-point composite response." The subjects who achieve the 2-point composite response will be abbreviated as "2-point composite responders."

## **Safety Endpoints**:

- Frequency, severity and relationship to study drug of treatment-emergent adverse events during the first four weeks post treatment and the overall study duration
- Frequency, severity and relationship to study drug of treatment-emergent serious adverse events during the first four weeks post treatment and the overall study duration

[figure not shown]
# 7.4 SUMMARIES OF TRIAL CONDUCT AND TREATMENT GROUP COMPARABILITY

The number of subjects randomized will be tabulated by trial center and treatment group. Subject disposition (the number of subjects randomized, treated, and completing each key trial visits) will be tabulated by treatment group. Premature study discontinuation and reasons for discontinuation will be summarized. Eligibility criteria deviations and other major protocol violations will be summarized.

Demographic and baseline characteristics will be summarized for all randomized subjects by treatment groups.

#### 7.5 EFFICACY ANALYSES

Unless specified otherwise, the main method of handling missing efficacy data will be

[figure not shown]
Descriptive statistics will be provided for all efficacy variables at all timepoints by treatment group. The point estimate of the treatment difference and 95% confidence interval (CI) of the difference (or 90% CI when the comparisons are 1-sided) will be generated.

[figure not shown]
#### 7.5.1 PRIMARY EFFICACY ENDPOINT

Primary clinical efficacy will be assessed by the blinded evaluator who will grade the severity of the subject's glabellar lines at maximum frown using the IGA-FWS and the subject who will grade the severity of their glabellar lines at maximum frown using the PFWS. A response is defined as achieving a score of 0 or 1 (none or mild) and an improvement of at least two points from the baseline, on both the IGA-FWS and PFWS scales concurrently at the time point of evaluation. With both IGA-FWS and PFWS using a 4-point scale and the target population having a score of 2 or 3 (moderate or severe) at baseline, achieving an improvement of at least two points is inclusive in the status of achieving a score of 0 or 1 (none or mild). Henceforth, the response defined here will be abbreviated as "2-point composite response."

The proportion of subjects who have a 2-point composite response at Week 4 will be compared between daxibotulinumtoxinA and placebo using the Cochran–Mantel–Haenszel (CMH) test stratified by trial center using a two-sided test with a Type I error rate of 0.05.

## 7.5.5 HANDLING MISSING DATA AND OTHER CONSIDERATIONS

Missing Data
For endpoints that are a composite and/or derived from study assessments, imputation of missing data will be performed on the original assessments first.
No imputations will be utilized for the PP analyses.
As needed, a model-based multiple imputation approach may be explored to assess the impact of different imputation methods on the trial outcomes.
Pooling Data
Most of the efficacy endpoints are analyzed with trial center as a stratification factor. The trial is intended to be conducted in a manner such that a minimum of 5 ITT subjects in each treatment group will be enrolled at each trial center/site. In the event that there are too few subjects in a treatment arm at a single site, this site will be combined with another to achieve the desired minimum sample size per arm.
7.5.6 SENSITIVITY AND SUBGROUP ANALYSES
The robustness of main analysis results for the primary and secondary endpoints will be evaluated via sensitivity analyses on the per-protocol population and on data with missing values imputed using different approaches, such as no imputation (observed data only) or when necessary, multiple imputation.
Statistical tests will be conducted to identify if there are extreme trial centers that could affect the interpretation of common statistical and clinical conclusions. A CMH test of the primary efficacy endpoint will be conducted with factors of treatment group stratified by trial center.

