### **Design and Methodology:**

This is a Phase 3, randomized, double-blind, placebo-controlled, multi-center trial. Approximately 300 adult subjects with moderate to severe glabellar lines will be enrolled. Subjects will be randomly assigned in a 2:1 ratio to DaxibotulinumtoxinA for Injection 40 U or placebo.

All subjects will be followed for at least 24 weeks post-treatment for efficacy and safety assessments. If both Patient Frown Wrinkle Severity (PFWS) and Investigator Global Assessment Frown Wrinkle Severity (IGA-FWS) scores at maximum frown, return to baseline by the Week 24 visit or at a visit between Weeks 24 and 36, the visit at which that score is recorded will be the Final Evaluation Visit for the subject.

After the Final Evaluation Visit, all qualified subjects will have the option to enroll into an open-label, trial to evaluate the long-term safety of repeat use of DaxibotulinumtoxinA for Injection for the treatment of moderate to severe glabellar lines.

The Investigator, trial center staff, subjects, and Sponsor will remain blinded to study treatment throughout the trial. Only the statistician responsible for the randomization codes will be unblinded to the treatment assignments.

Treatment Group	Test Article and Dose	No. of Subjects	
Treatment 1	DaxibotulinumtoxinA for Injection 40 U	200	
Treatment 2	Placebo	100	

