## 7.7 SAMPLE SIZE AND POWER CONSIDERATIONS

Estimates of treatment efficacy taken from trial RT002-CL002 show that a sample size of
200 and 100 for DaxibotulinumtoxinA 40 U for injection and placebo, respectively,

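### Per-protocol or observed-data-only results at Weeks 28 to 36 would rest on a set enriched for persisting effect, because planned exit follows return to baseline

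*Protocol*

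**What the plan says.** **Planned exit.** Visits are scheduled to Week 36. Under the Protocol Synopsis (Design and Methodology), once both PFWS and IGA-FWS at maximum frown are back at baseline at Week 24 or later, "the visit at which that score is recorded will be the Final Evaluation Visit for the subject". Protocol 4.2.5 ends participation at that visit if there is no safety concern, and SAP 2.1 gives the same follow-up rule.

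**Timepoints.** Protocol 7.5: "Descriptive statistics will be provided for all efficacy variables at all timepoints by treatment group". SAP 4.6 repeats this.

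**No-imputation analyses.** Protocol 7.5.5: "No imputations will be utilized for the PP analyses". Protocol 7.5.6 checks the robustness of the primary and secondary results in the per-protocol (PP) population and under other ways of handling missing values, "such as no imputation (observed data only) or when necessary, multiple imputation".

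**PP membership.** Protocol 7.2 and SAP 4.1.2 define it by the first four weeks, so a subject who exits at Week 24 or later still belongs to the PP population.

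**What cannot be seen.** The main missing-data method in Protocol 7.5 and the definitions of the secondary endpoints are redacted. No visible text says how a subject who has left by planned exit counts at later visits.

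**The concern.** The scores that trigger exit are the efficacy scores themselves. A subject who has left by this route had no improvement on either scale at the last visit and so could not be a 2-point composite responder there. A later analysis that uses only recorded values drops that subject from numerator and denominator alike. Those who stay are disproportionately those in whom some effect persists.

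At stake are the late response percentages and mean scores in PP and observed-only tables, and the use of those tables as a check on any result that reaches past Week 24. The PP rule in 7.5.5 carries no exception. The main method in 7.5 applies only where nothing else is specified, so even a suitable redacted default would, as 7.5.5 is worded, be switched off for PP.

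**Working it through.** **1. The plan's own figure.** The Synopsis gives about 300 subjects allocated 2:1. 300 × 2/3 = 200 and 300 × 1/3 = 100, which agrees with the stated group sizes. Power cannot be rebuilt because the assumed rates and the power are redacted. The documents state no figure for Weeks 28 to 36.

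**2. Relation.** Let r be the response rate among all treated subjects in an arm at a late visit, and e the share that left by planned exit at an earlier visit. Assume that exited subjects remain non-responders, and ignore other dropout. All responders are then among those still observed:

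observed-only rate = r / (1 − e)

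**3. Active arm at Week 28** (N = 200; r = 10% and e assumed, giving 200 × 0.10 = 20 responders):

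| Exited at Week 24 | Still observed | Observed-only rate | Factor |
|---|---|---|---|
| 30% | 140 | 20/140 = 14.3% | 1.43 |
| 50% | 100 | 20/100 = 20.0% | 2.00 |
| 70% | 60 | 20/60 = 33.3% | 3.33 |

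**4. Placebo arm at Week 28** (N = 100; r = 1% and e assumed, giving 1 responder). A placebo subject who never changed is at baseline on both scales at Week 24, so high exit is plausible.

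| Exited at Week 24 | Still observed | Observed-only rate | Per centre, 15 centres |
|---|---|---|---|
| 80% | 20 | 1/20 = 5% | 1.3 |
| 90% | 10 | 1/10 = 10% | 0.7 |
| 95% | 5 | 1/5 = 20% | 0.3 |

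Protocol 7.5.5 stratifies most efficacy endpoints by centre and aims for at least 5 ITT subjects per arm at each centre. That minimum counts subjects enrolled, not those still observed, so a late stratified comparison would have almost empty placebo strata.

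**5. Treatment difference** (active minus placebo, all rates assumed):

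| r, active / placebo | Exited, active / placebo | All treated | Observed-only |
|---|---|---|---|
| 10% / 1% | 50% / 90% | 9 points | 20.0 − 10.0 = 10.0 |
| 20% / 1% | 30% / 80% | 19 points | 28.6 − 5.0 = 23.6 |
| 10% / 2% | 50% / 90% | 8 points | 20.0 − 20.0 = 0 |
| 10% / 2% | 70% / 95% | 8 points | 33.3 − 40.0 = −6.7 |

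Each arm's rate moves up. The difference can widen, vanish or reverse.

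**The case against.** Four stronger readings are tempting, and the documents do not support them.

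- *The plan classes planned exit as missing data.* No visible text says so. Protocol 4.2.5 treats the Final Evaluation Visit as completion, and 4.2.6 deals separately with leaving before it. The visible text is silent on how completers count later, and redacted text may cover it.
- *Late results come only from subjects still benefiting.* Exit needs both scales at baseline, and the exit visit is itself recorded. The Week 28 set therefore includes subjects whose return is recorded that day, subjects back at baseline on one scale only, and subjects with some improvement but no response. It is enriched for benefit, not limited to it.
- *The comparison is biased in favour of the drug.* Placebo rates are inflated too, possibly by more, and the last table in the working shows differences moving both ways.
- *The trial's main efficacy conclusions are at risk.* The primary endpoint is at Week 4, 20 weeks before any planned exit. Whether a secondary endpoint uses Weeks 28 to 36 cannot be seen. The abbreviation list includes Kaplan-Meier. In a time-to-return analysis the exit visit would record the event, so planned exit would lose nothing.

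Two further objections have some force. The all-timepoints sentence in 7.5 does not say that its summaries are PP or observed-only, and 7.5.6 offers observed data as one example of an approach, so the point is conditional on such analyses reaching the late visits. Also, carrying the exit scores into an observed-data table means that it no longer holds only measurements. That is so, but non-response at exit is recorded, whereas leaving these subjects out selects on the outcome.

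What does not fall away is the unqualified PP rule. Followed as written at a late visit, it gives the selected result whatever the redacted default says.

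**Conclusion.** The point holds in a limited form: any PP or observed-data-only analysis of Weeks 28, 32 or 36 would overstate the response rate in each arm by 1/(share remaining). Under assumed exit of 30% to 70% this is a factor of 1.43 to 3.33. Under assumed placebo exit of 80% to 95%, only 5 to 20 of 100 placebo subjects would remain. The direction of bias in the treatment difference is not fixed, which by itself makes such an analysis a poor robustness check.

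The size rests on assumed exit and response rates, on exited subjects staying non-responders, and on ignoring other dropout. The mechanism rests on visible text. The point says nothing about the redacted main analysis and leaves the Week 4 primary result untouched. It is a moderate matter of late-visit reporting.

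**What to change.** In Protocol 7.5.5 and 7.5.6 and in the SAP, state that a subject who completes by planned exit, with both scales back at baseline, is not missing. In any PP or observed-data analysis of Weeks 28 to 36, that subject stays in the denominator at later scheduled visits as a non-responder, with the exit (baseline) scores carried. Only other absences are treated as missing. Word the PP no-imputation sentence so that it does not exclude this derivation. Report the number still under observation by arm at Weeks 28, 32 and 36. If redacted text already contains such a rule, a cross-reference that extends it to the PP and observed-data analyses is enough.

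The cost is one derivation flag and a few lines of text, with no new data and no change in conduct. Late response percentages will look less favourable.
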